10.3 Responsibilities of the investigator and IRB/IEC

Before initiating a trial, the investigator/institution must obtain approval/favorable opinion from the Institutional Review Board/Independent Ethics Committee (IRB/IEC) for the trial protocol, written informed consent form, consent form updates, participant recruitment procedures (e.g., advertisements) and any other written information to be provided to participants. Prior to study start, the investigator is required to sign a protocol signature page confirming his/her agreement to conduct the study in accordance with these documents and all of the instructions and procedures found in this protocol and to give access to all relevant data and records to Novartis monitors, auditors, Novartis Quality Assurance representatives, designated agents of Novartis, IRBs/IECs, and regulatory authorities as required. If an inspection of the clinical site is requested by a regulatory authority, the investigator must inform Novartis immediately that this request has been made.

10.4 Publication of study protocol and results

The key design elements of this protocol will be posted in a publicly accessible database such as clinicaltrials.gov. In addition, upon study completion and finalization of the study report the results of this trial will be either submitted for publication and/or posted in a publicly accessible database of clinical trial results.

10.5 Quality Control and Quality Assurance

Novartis maintains a robust Quality Management (QM) system that includes all activities involved in quality assurance and quality control, including the assignment of roles and responsibilities, the reporting of results, and the documentation of actions and escalation of issues identified during the review of quality metrics, incidents, audits and inspections.

Audits of investigator sites, vendors, and Novartis systems are performed by Novartis Pharma Auditing and Compliance Quality Assurance, a group independent from those involved in conducting, monitoring or performing quality control of the clinical trial. The clinical audit process uses a knowledge/risk based approach.

Audits are conducted to assess GCP compliance with global and local regulatory requirements, protocols and internal SOPs, and are performed according to written Novartis processes.

11 Protocol adherence

This protocol defines the study objectives, the study procedures and the data to be collected on study participants. Additional assessments required to ensure safety of participants should be administered as deemed necessary on a case by case basis. Under no circumstances is an investigator allowed to collect additional data or conduct any additional procedures for any research related purpose involving any investigational drugs under the protocol.

Investigators ascertain they will apply due diligence to avoid protocol deviations. If an investigator feels a protocol deviation would improve the conduct of the study this must be considered a protocol amendment, and unless such an amendment is agreed upon by Novartis and approved by the IRB/IEC and health authorities, where required, it cannot be implemented.

13.1 Clinically notable test values and vital signs

13.1.1 Vital signs

Table 13-1 Clinically notable vital signs

Variable	Change relative to baseline		
Heart Rate	> 120 bpm < 50 bpm	and an and a	increase of \geq 15 bpm decrease of \geq 15 bpm
Systolic BP	> 180 mm Hg < 90 mm Hg	and an and a	increase of \geq 20 mm Hg decrease of \geq 20 mm Hg
Diastolic BP	> 105 mm Hg < 50 mm Hg	and an and a	increase of \geq 15 mm Hg decrease of \geq 15 mm Hg
Weight			change of \geq +/- 7%

13.1.2 Clinically notable ECG and laboratory values

Abnormal ECG values will be specified in the manual from the centralized ECG vendor, with specific telephone alert values and panic alert values.

Figure 13-1 Abnormal ECG measurements leading to exclusion alerts

Category	Values leading to exclusion alerts
HR_MN	< 40 or > 120
Mean QRS interval	> 140 ms
Mean QTcF interval	> 500 ms

Abnormal laboratory values will be specified in the manual from the central laboratory with specific telephone alert values and panic alert values.

The Novartis Medical Monitor will be notified by email and fax at the same time as the investigator for all types of alerts.

Discontinuation of study medication, for individual participant, is required in case of clinically significant ECG or laboratory findings considered to be suspected to be related to study medication, as judged by Investigator or the DMC, respectively.

Table 13-2 Abnormal laboratory values leading to participant exclusion

Organ	Laboratory value	Limits
Liver	ALT or AST	> 5 × ULN
	ALP	> 2 × ULN (in the absence of known bone pathology)
	TBL	> 2 × ULN (in the absence of known Gilbert syndrome)
	ALT or AST and INR	> 3 × ULN and > 1.5

Organ	Laboratory value	Limits
Renal	Estimated glomerular filtration rate (GFR)	<30mL/min (calculated using the Cockcroft-Gault formula)
Blood (chemistry)	Calcium (mg/dL)	<7.0; >12.5
	Phosphorus (mg/dL)	<2.0
	Sodium (mmol/L)	<125; >155
	Potassium (mmol/L)	<3.0; >6.0
Blood (Hematology)	Magnesium (mg/dL)	>3.0
	HGB (g/dL)	<8.0; ≥19.0
	WBC (GI/L)	<2.0; ≥13.0
	Platelets (GI/L)	<50; ≥700

13.2 Neurological symptoms or signs

New neurological findings are defined as clinical signs or symptoms that raise concern in respect to neurological conditions.

They include but are not limited to:

- significant new or worsening neurological symptoms or signs, as reported spontaneously by the participants/caregivers at any time, or detected during the scheduled physical/neurological examinations or on MRI scans. These might be events such as new or worsening peripheral neuropathies, visual disturbances, or seizures;
- worsening of cognition not consistent with the previous clinical course, as reported spontaneously by the participants/caregivers at any time or observed at the clinical assessments (e.g. APCC, CDR-SOB, RBANS, NPI-Q).

Investigators will be asked to review the finding in consultation with an appointed neurologist (when applicable) and initiate any additional tests as needed. Summary of the findings will be provided for the attention of the Safety Monitor who will assess the need to consult the DMC, regardless of the suspected relationship to investigational treatment.

Further tests will be scheduled to monitor the time-course of the findings until resolution if possible, and detailed information on the results will be communicated to the DMC.

Discontinuation of study medication will be considered in case of clinically significant findings considered to be suspected to be related to study medication, as judged by investigator and DMC.

These findings will be reported additionally as AEs only if they are symptomatic (i.e. reported spontaneously and not only observed at scheduled assessments), require symptomatic treatment, or impact study medication (suspension or discontinuation).

In case MRI findings indicating CNS inflammation, additional clinical investigations including physical and neurological examinations and laboratory evaluations will be performed. Final interpretation of the safety MRI scans, including assessment of ARIA, white matter, stroke or other findings will be provided to the site by the Imaging vendor.

13.3 Liver and renal event and laboratory trigger definitions and follow-up requirements

Note: Tests below are recommended to be performed at a local lab for a faster result availability. However, if required exception testing by central lab can also be organized even if they are not part of the regular laboratory testing.

Table 13-3 Liver Event and Laboratory Trigger Definitions

	Definition/ threshold
LIVER LABORATORY TRIGGERS	$3 \times \text{ULN} < \text{ALT} / \text{AST} \leq 5 \times \text{ULN}$ $1.5 \times \text{ULN} < \text{TBL} \leq 2 \times \text{ULN}$
LIVER EVENTS	ALT or AST $> 5 \times \text{ULN}$ ALP $> 2 \times \text{ULN}$ (in the absence of known bone pathology) TBL $> 2 \times \text{ULN}$ (in the absence of known Gilbert syndrome) ALT or AST $> 3 \times \text{ULN}$ and INR > 1.5 Potential Hy's Law cases (defined as ALT or AST $> 3 \times \text{ULN}$ and TBL $> 2 \times \text{ULN}$ [mainly conjugated fraction] without notable increase in ALP to $> 2 \times \text{ULN}$) Any clinical event of jaundice (or equivalent term) ALT or AST $> 3 \times \text{ULN}$ accompanied by (general) malaise, fatigue, abdominal pain, nausea, or vomiting, or rash with eosinophilia Any adverse event potentially indicative of a liver toxicity*

*These events cover the following: hepatic failure, fibrosis and cirrhosis, and other liver damage-related conditions; the non-infectious hepatitis; the benign, malignant and unspecified liver neoplasms

TBL: total bilirubin; ULN: upper limit of normal

Table 13-4 Follow-up requirements for liver events and laboratory triggers

Criteria	Actions required	Follow-up monitoring
Potential Hy's Law case ^a	Discontinue the study treatment immediately Hospitalize, if clinically appropriate Establish causality Complete liver CRF	ALT, AST, TBL, Alb, PT/INR, ALP and γ GT until resolution ^c (frequency at investigator discretion)
ALT or AST		
$> 8 \times \text{ULN}$	Discontinue the study treatment immediately Hospitalize if clinically appropriate Establish causality Complete liver CRF	ALT, AST, TBL, Alb, PT/INR, ALP and γ GT until resolution ^c (frequency at investigator discretion)
$> 3 \times \text{ULN}$ and INR > 1.5	Discontinue the study treatment immediately Hospitalize, if clinically appropriate Establish causality Complete liver CRF	ALT, AST, TBL, Alb, PT/INR, ALP and γ GT until resolution ^c (frequency at investigator discretion)

Criteria	Actions required	Follow-up monitoring
> 5 to ≤ 8 × ULN	Repeat LFT within 48 hours If elevation persists, continue follow-up monitoring If elevation persists for more than 2 weeks, discontinue the study drug Establish causality Complete liver CRF	ALT, AST, TBL, Alb, PT/INR, ALP and γGT until resolution ^c (frequency at investigator discretion)
> 3 × ULN accompanied by symptoms ^b	Discontinue the study treatment immediately Hospitalize if clinically appropriate Establish causality Complete liver CRF	ALT, AST, TBL, Alb, PT/INR, ALP and γGT until resolution ^c (frequency at investigator discretion)
> 3 to ≤ 5 × ULN (participant is asymptomatic)	Repeat LFT within the next week If elevation is confirmed, initiate close observation of the participant	Investigator discretion Monitor LFT within 1 to 4 weeks
ALP (isolated)		
> 2 × ULN (in the absence of known bone pathology)	Repeat LFT within 48 hours If elevation persists, establish causality Complete liver CRF	Investigator discretion Monitor LFT within 1 to 4 weeks or at next visit
TBL (isolated)		
> 2 × ULN (in the absence of known Gilbert syndrome)	Repeat LFT within 48 hours If elevation persists, discontinue the study drug immediately Hospitalize if clinically appropriate Establish causality Complete liver CRF	ALT, AST, TBL, Alb, PT/INR, ALP and γGT until resolution ^c (frequency at investigator discretion) Test for hemolysis (e.g., reticulocytes, haptoglobin, unconjugated [indirect] bilirubin)
> 1.5 to ≤ 2 × ULN (participant is asymptomatic)	Repeat LFT within the next week If elevation is confirmed, initiate close observation of the participant	Investigator discretion Monitor LFT within 1 to 4 weeks or at next visit
Jaundice	Discontinue the study treatment immediately Hospitalize the participant Establish causality Complete liver CRF	ALT, AST, TBL, Alb, PT/INR, ALP and γGT until resolution ^c (frequency at investigator discretion)
Any AE potentially indicative of a liver toxicity*	Consider study treatment interruption or discontinuation Hospitalization if clinically appropriate Establish causality Complete liver CRF	Investigator discretion

^aElevated ALT/AST > 3 × ULN and TBL > 2 × ULN but without notable increase in ALP to > 2 × ULN

^b(General) malaise, fatigue, abdominal pain, nausea, or vomiting, or rash with eosinophilia

^cResolution is defined as an outcome of one of the following: (1) return to baseline values, (2) stable values at three subsequent monitoring visits at least 2 weeks apart, (3) remain at elevated level after a maximum of 6 months, (4) liver transplantation, and (5) death.

Table 13-5 Specific Renal Alert Criteria and Actions

Serum Event	
Serum creatinine increase 25 – 49% compared to baseline	Confirm 25% increase after 24-48h Follow up within 2-5 days
Acute Kidney Injury: Serum creatinine increase ≥ 50% compared to baseline	Follow up within 24-48h if possible Consider study treatment interruption Consider participant hospitalization /specialized treatment
Urine Event	
New dipstick proteinuria ≥1+ Albumin- or Protein-creatinine ratio increase ≥2-fold Albumin-creatinine ratio (ACR) ≥30 mg/g or ≥3 mg/mmol; Protein-creatinine ratio (PCR)≥150 mg/g or >15 mg/mmol	Confirm value after 24-48h Perform urine microscopy Consider study treatment interruption / or discontinuation
New dipstick glycosuria ≥1+ not due to diabetes	Blood glucose (fasting) Perform serum creatinine, ACR
New dipstick hematuria ≥1+ not due to trauma	Urine sediment microscopy Perform serum creatinine, ACR
For all renal events:	

Document contributing factors in the CRF: co-medication, other co-morbid conditions, and additional diagnostic procedures performed
 
Monitor participant regularly (frequency at investigator’s discretion) until either:
 
Event resolution: sCr within 10% of baseline or protein-creatinine ratio within 50% of baseline, or
 
Event stabilization: sCr level with ±10% variability over last 6 months or protein-creatinine ratio stabilization at a new level with ±50% variability over last 6 months.
	

14 Appendix 2: Role of study partner and key site personnel

Study partner

The study partner is expected to spend sufficient time with the participant to be familiar with his/her overall function and behavior, and be able to provide adequate information about the participant including: (a) knowledge of domestic activities, hobbies, routines, social skills and basic activities of daily life; (b) work and educational history; (c) cognitive performance, including memory abilities, language abilities, temporal and spatial orientation, judgment, and problem solving; (d) emotional and psychological state; and (e) general health status.

Although the study partner is expected to accompany the participant to all relevant visits, if unavailable to attend a given site visit (e.g. if traveling or sick), his/her input to clinical scales can be organized via a telephone interview [REDACTED]. Yet for CDR and ECog, a site visit is preferable

The study partner and/or the participant will be requested to call the site to inform about any study partner unavailability or transition to a new one. Of note: a study partner needs to be identified and documented before the next study treatment dispensing visit, otherwise the study treatment would be suspended until a new partner is identified.

The study partner is excluded from participating in any study in the Generation Program (CCAPI015A2201J and CCNP520A2202J). The study partner may only be a participant if another study partner can be identified. A participant cannot act as study partner for another participant.

Key study personnel

Key site personnel include (but are not limited to) the following individuals:

Investigator

The investigator will be responsible for:

- Overall conduct of the study at the study site including assigning per protocol required study site personnel
- Organization of the referral and recruitment strategies at the site level (see also [Appendix 4](#))
- Organizing for the genetic disclosure as per local regulations if not done by genetic counselor (see below genetic counselor description)
- Organizing for the disclosure of the Amyloid status test results to the participants after receiving the results on elevated or non-elevated status from the centralized assessment performed by the central reader at the Imaging vendor.
Of note: the local read should never be communicated to the participant.
- Management of the routine clinical care of the study participants
- Confirmation of participant's eligibility for randomization
- Supervision of study drug dispensing. The investigator may delegate this responsibility to the Study Nurse/Study Coordinator as appropriate and permissible by local regulation

- Oversight of the raters performing the clinical assessments, review and interpretation of the results to support diagnosis of MCI or dementia. Timely completion of diagnosis verification form on the Virgil tablet.
- Management of adverse events and treatment decisions
- Ensuring that all site personnel are informed of concomitant medications excluded per protocol (see [Section 5.5.8](#))

- [REDACTED]

Occasionally, the investigator may designate other medical personnel/health care professionals (other than the Independent CDR rater, e.g., a back-up physician or Study Nurse/Study Coordinator) at the study site to perform some of the tests and evaluations listed above. The investigator is also responsible for ensuring access to appropriate expertise for consultation (e.g. dermatological findings, ECG interpretation, mental health care) during the study as needed.

Study Nurse/Study Coordinator (SC)

The Study Nurse/Study Coordinator's responsibilities may include:

- Assisting the investigator in participant management, including the assessment and treatment of adverse events, symptom progression and the recording of adverse events, concomitant medications and monitoring of compliance (counting of remaining capsules left over in bottles returned by the participant, uploading data from the electronic cap)
- Scheduling visits and assessments as outlined in the protocol, maintaining proper source documentation and transcription of the data to the CRFs
- Coordination with and between the study selected central labs, drawing, processing and shipping lab and biomarker samples
- Providing participant with an Information Card (identifying study participant in a clinical trial with pertinent information and site contact information)
- Entering data in the eCRF
- Retrieving required source information from the other units or departments (Radiology, Nuclear Medicine, lumbar puncture, Genetic counseling...)
- Performing ECG and uploading results to the central cardiology vendor
- Placing calls to IRT upon screening, randomization and drug dispensing visits, or PPW/EoT
- Administering the Virgil tablets: registering raters and participants and visits on the Cognition vendor portal.
- Coordinating the completion of the eC-SSRS on the ERT website

Genetic counselor

- Providing the genetic counseling about risk estimates for AD based on genotype for APOE, along with epidemiology and latest information available, using the standardized talking points and AD risk estimate materials provided at the study level.

- The genetic counselor as well as the rater who assesses the psychological readiness with GDS and STAI-AD before disclosure are expected to be blind to the actual APOE4 genotype for the participant until disclosure occurs.
- Once readiness of the participant to receive their individual information is confirmed, the counselor will obtain the genotype result and disclose it to the participant.
- Confirming to the SC that disclosure occurred and/or follow-up steps required.

Raters

Raters will be certified by the cognition vendor based on their qualifications and previous experience in rating the APCC scales. Training may be required in addition at study start, and regular re-training will also occur during the course of the study.

The initial MMSE at first Screening visit to verify a score >24 for inclusion can be performed by a non-certified rater (eg. Study Nurse or Study Coordinator) and be performed on paper not transcribed to the Virgil tablet in such case. Other scales which are not contributing to the APCC can also be administered by a non-certified rater or by the CDR rater.

Requirement for separate raters:

At least three different raters are needed for any given cognitive assessment: a CDR rater, a rater for other APCC scales, a physician to complete the diagnostic evaluation. The certified raters at the site will administer the clinical scales using the tablet provided by the Cognition vendor.

A separate rater for CDR scale is required, so that CDR rating is blinded to the other APCC scales' results.

The physician who completes the diagnostic evaluation form should not have administered the CDR at that given visit.

MRI technician

The MRI technician will be responsible for:

- Familiarization with the MRI manual procedures and the study specific MRI protocol
- Proceeding with the calibration and qualification steps required by Imaging vendor
- Performance of high-quality MRI scans using the study specific parameters stored in the designated MRI scanner for the duration of the study
- Submission of the MRIs in the appropriate format to the Imaging vendor for assessment by the central MRI reader

Nuclear Medicine Specialists

The NM technician will be responsible for:

- Familiarization with the PET manual procedures and the study specific PET protocol for amyloid radiotracer(s) available for the site
- Proceeding with the calibration and qualification steps required by Imaging vendor

[figure not shown]
- Performance of high-quality PET scans using the study specific parameters stored in the designated PET scanner for the duration of the study
- Submission of the PET scans in the appropriate format to the Imaging vendor for centralized assessment.

Of note: local evaluation SHOULD never be communicated to the participant.

Lumbar Puncture specialist

Lumbar punctures should be performed by a qualified and experienced specialist (e.g. anesthesiologist or physician) with regular practice of lumbar punctures.

The procedure and details on possible side-effects and minimization methods will be described to the participant upfront.

16 Appendix 4: Recruitment methods

It is anticipated that there will be different methods of recruitment, with site and/or country specificity. Some potential participants will already be part of a local/regional/national registry. Some potential participants will be known to investigators as the relatives of affected participants. Some may be self-referred from an initial assessment/memory check (e.g. subjective complains or concern due to familial history) or because they are already aware of their APOE4 genotype (e.g. from private genetic testing companies).

Additionally, country specific programs may potentially be offered. For example, in the US, potential participants may be referred to a trial-independent APOE genotyping program. This program will apply an algorithm to invite APOE4 carriers (HMs and HTs) and non-carriers that meet basic eligibility criteria to participate in this study.

Table 16-1 Referral source of participants

Referral method	Participants referred for screening part I and genetic disclosure
1) Potential participants with previous genotype information and genetic disclosure performed in the API015A2201J study	HTs will still have to undergo amyloid testing and disclosure in screening part II. See Section 6.1.2
2) Pre-existing registries/local databases with available and previously disclosed genotype information, as per local clinical practice; informed consent allows for re-contact for potential clinical trial participation based on the genotype.	HTs and HMs will be invited to the screening part I including the genetic counseling and disclosure despite their genotype knowledge to ensure the same process and counseling steps are followed. The buccal swab will need to be repeated at the study central laboratory even with appropriate confirmed documentation of genotype. See more information in Section 6.1.2
3) Pre-existing registries/local databases with available but not disclosed genotype information; informed consent allows for re-contact.	HTs, HMs and a sufficient proportion of non-carriers will be invited to attend the screening visit part I. The exact ratio of each genotype will not be disclosed to the participants in order to prevent implicit disclosure by invitation. During the initial contact with participants inviting them to the screening part I, it must be highlighted that those with and without the genotype of interest are invited at this stage. See more information in Section 6.1.2
4) De novo genotyping: Newly identified potential participants, without prior genotype information.	The investigator will assess the most efficient way* to identify HMs and HTs to build a local database according to the local regulations and in collaboration with the Sponsor. A buccal swab will be performed to obtain the APOE genotype under the preliminary informed consent ICF#A. The genotyping will be performed at the central laboratory. The site will identify a dedicated recipient of the genotype results as described above for scenario 3. Not all participants that perform the genetic testing will be disclosed*.

*The process will be documented in the local study file. Such a process will be site/country-specific. The person delivering the genetic counseling and disclosure should be qualified according to local regulations

APOE4 = Apolipoprotein E4; HM = homozygote; HT= heterozygote.

17 Appendix 5: A testing strategy with option for dose regimen modification and two endpoints

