6.4.4.1 Hematology

A standard hematology panel with differential counts will be performed. Hemoglobin (Hb), hematocrit, red blood cell count, platelet count, and white blood cell count with differential count will be measured.

In addition if clinically warranted for participants treated with anti-coagulants, prothrombin time international normalized ratio (PT/INR) may be measured for assessment of coagulation at screening and repeated, if required.

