6.4.4.2 Clinical chemistry

A standard blood chemistry panel will be performed: Albumin, total protein, alkaline phosphatase, total bilirubin, calcium, chloride, sodium, potassium, magnesium, inorganic phosphorus, bicarbonate, creatinine, creatine phosphokinase (CPK), C-reactive protein (CRP), Vitamin B12, folate, gamma-glutamyl transferase (γ -GT), lactate dehydrogenase (LDH), cholesterol (total / LDL / HDL), triglycerides, lipase, α -amylase, alanine aminotransferase (ALT), aspartate aminotransferase (AST), glycated hemoglobin (HbA1c), blood urea nitrogen (BUN), uric acid, and thyroid stimulating hormone (TSH) will be measured.

The creatinine clearance will be estimated from serum creatinine concentrations using the Cockcroft-Gault formula. The results should be available and reviewed before the MRI scans if gadolinium injection is required because of findings on previous MRI scans.

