7.3 Liver safety monitoring

To ensure participant safety and enhance reliability in determining the hepatotoxic potential of an investigational drug, a standardized process for identification, monitoring and evaluation of liver events has to be followed.

The following two categories of abnormalities / adverse events have to be considered during the course of the study (irrespective of whether classified/reported as (S)AE):

- Liver laboratory triggers, which will require repeated assessments of the abnormal laboratory parameter
- Liver events, which will require close observation, follow-up monitoring and completion of the standard base liver CRF pages

Every liver laboratory trigger or liver event as defined in [Section 13.3](#) should be followed up by the investigator or designated personal at the trial site as summarized below. Detailed information is outlined in [Table 13-3](#) and [Table 13-4](#) in [Appendix 1](#).

For the liver laboratory trigger:

- Repeating the liver function test (LFT) within the next week to confirm elevation.
- These LFT repeats must be performed using the central laboratory if possible. If this is not possible, then the repeats can be performed at a local laboratory to monitor the safety of the participant. Repeat LFTs must then be performed at central laboratory as soon as possible. If a liver event is subsequently reported, any local LFTs previously conducted that are associated with this event must be reported on the Liver CRF pages.
- If the elevation is confirmed, close observation of the participant will be initiated, including consideration of treatment interruption if deemed appropriate.
- For the liver events:

- Repeating the LFT to confirm elevation as appropriate
- Discontinuation of the investigational drug if appropriate
- Hospitalization of the participant if appropriate
- A causality assessment of the liver event via exclusion of alternative causes (e.g., disease, co-medications)
- An investigation of the liver event which needs to be followed until resolution.
- These investigations can include serology tests, imaging and pathology assessments, consultancy of a hepatologist, based on investigator's discretion. All follow-up information, and the procedures performed must be kept as source and recorded on appropriate CRF pages, including the liver event overview CRF pages.

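### Protocol Table 13-4 makes INR > 1.5 a mandatory stop when ALT or AST exceeds 3×ULN, but does not require INR in the one band where that criterion alone creates a liver event

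*Protocol*

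**What the plan says.** Protocol Table 13-3 lists ALT or AST > 3×ULN with INR > 1.5 as a liver event, and SAP Table 5-2 repeats it for reporting. For that criterion the first action in Protocol Table 13-4 is "Discontinue the study treatment immediately".

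The row headed "> 3 to ≤ 5 × ULN (participant is asymptomatic)" is handled differently. It asks for a repeat LFT within a week, close observation if the rise is confirmed, and LFT monitoring in 1 to 4 weeks at the investigator's discretion. PT/INR is not named.

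Other sections that bear on whether INR is measured in this band:

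- Section 7.3 describes "Liver laboratory triggers, which will require repeated assessments of the abnormal laboratory parameter". For a confirmed trigger it asks for close observation, "including consideration of treatment interruption if deemed appropriate".
- Section 6.4.4.1 says that "if clinically warranted for participants treated with anti-coagulants, prothrombin time international normalized ratio (PT/INR) may be measured".
- Section 6.4.4.2 begins "A standard blood chemistry panel will be performed"; the analytes it lists do not include INR.
- Section 6.1.3 requires PT/INR only at screening, for participants consenting to lumbar puncture.
- The note opening Section 13.3 recommends a local laboratory for speed and adds that "if required exception testing by central lab can also be organized even if they are not part of the regular laboratory testing".

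**The concern.** A stopping rule with two inputs works only if both are measured. In this band the enzyme result is known and the INR may not be. An asymptomatic participant at 4×ULN would be repeated and observed, and perhaps interrupted if the investigator chose, without the test that would make stopping mandatory.

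Reporting has the matching weakness. SAP Section 2.1 takes percentages in population-level summaries over all participants in the group. Unless the table shells (not available) say otherwise, a participant in this band with no INR would appear alongside those whose INR was normal.

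**Working it through.** There is no sample size, power or alpha figure to reproduce. The check is on the logic of the criteria and on the rows of Table 13-4.

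**Step 1. Where can the INR criterion create a liver event by itself?** The inputs are the criteria in Protocol Table 13-3, repeated in SAP Table 5-2. ALT or AST > 5×ULN is already a liver event. So are > 3×ULN with the listed symptoms, TBL > 2×ULN, ALP > 2×ULN, Hy's Law and jaundice.

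Take INR > 1.5 and cross three ALT/AST bands (> 3 to 5, > 5 to 8, > 8×ULN) with symptoms present or absent, giving 3 × 2 = 6 groups. Within each group, cross three TBL levels (not raised, > 1.5 to 2, > 2×ULN), two ALP levels (≤ 2, > 2×ULN) and jaundice (no, yes), giving 3 × 2 × 2 = 12 combinations.

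- > 3 to ≤ 5×ULN without symptoms: INR is the sole trigger in 2 of 12 combinations (TBL ≤ 2×ULN at two levels × ALP ≤ 2×ULN × no jaundice = 2 × 1 × 1).
- Each of the other five groups: 0 of 12.

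These counts locate the band; they are not probabilities. The open-ended criterion for adverse events suggesting liver toxicity is left out. The exceptions for known Gilbert syndrome and bone pathology do not move the band, because > 5×ULN and symptoms above 3×ULN are events in their own right.

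**Step 2. Which rows of Table 13-4 name PT/INR?**

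| Row with ALT/AST > 3×ULN | Immediate stop without INR? | PT/INR named? |
|---|---|---|
| a. Potential Hy's Law | Yes | Yes |
| b. > 8×ULN | Yes | Yes |
| c. > 3×ULN and INR > 1.5 | This is the INR criterion | Yes |
| d. > 5 to ≤ 8×ULN | No | Yes |
| e. > 3×ULN with symptoms | Yes | Yes |
| f. > 3 to ≤ 5×ULN, asymptomatic | No | No |

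Five of six rows name PT/INR. Rows a, b and e (3) stop without it and row c (1) is the criterion itself, leaving 6 − 3 − 1 = 2 rows, d and f, where an INR result would change the action. Row d otherwise says "If elevation persists for more than 2 weeks, discontinue the study drug", so INR > 1.5 would bring the stop forward; PT/INR is named there. Row f is the remaining gap, and it is the band found in Step 1.

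**Step 3. Does another section require INR in row f?** No. Section 7.3 repeats the abnormal parameter, which is the enzyme. Section 6.4.4.1 is optional and concerns anticoagulated participants. The Section 6.4.4.2 panel omits INR, and Section 6.1.3 applies at screening. The Section 13.3 note deals with where tests are run and adds none to a row.

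**Step 4. Would a discretionary INR reach the database?** Not reliably. Row f is the only one of the six without an instruction to complete the liver CRF. Section 7.3 requires earlier local LFTs on the liver CRF pages only if a liver event is later reported. A normal INR from a local laboratory in this band therefore has no specified route into the data.

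**The case against.** The strongest defence is that the omission fits the tiering. Asymptomatic 3 to 5×ULN is a laboratory trigger, not a liver event, and the parallel TBL trigger row (> 1.5 to ≤ 2×ULN) also asks only for a repeat, observation and discretion. Confirming first and escalating later is a reasonable design. What this does not answer is that the same table attaches an immediate stop to an INR result in this band, so INR is needed to know which tier the participant is in.

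A second defence is that LFT may include INR. That is possible, since the protocol expands the term only as liver function test and the Laboratory Manual is not available. The text gives it little support: PT/INR sits under hematology rather than chemistry, and row d names it separately from the LFT repeat.

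Third, anticoagulants are allowed (Protocol Table 5-2), and an INR above 1.5 in such a participant may have no hepatic cause. Table 5-1 already restricts warfarin, which narrows the group without removing it. This objection stands, and the fix has to deal with it.

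Three stronger readings are tempting and not supported:

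- A reader might infer that participants in this band are unprotected. INR may be ordered and treatment interrupted, and Sections 5.6.2 and 13.1.2 separately require stopping for clinically significant laboratory findings suspected to be drug-related.
- A reader might infer that the report could be repaired by counting who had an INR. Step 4 shows why not: a participant with a normal local result could be counted as untested.
- A reader might take the absence of INR from SAP Tables 5-7 and 5-8 as a sign that it was overlooked. Those tables cover selected tests, and the INR criterion is in SAP Table 5-2.

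**Conclusion.** The point holds, and it is minor. Following the protocol as written leaves one mandatory stopping criterion without a required input in one row out of six, in the only band where that criterion alone makes a liver event. INR is not mandated there, but it is not forbidden.

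The conclusion assumes that LFT does not include INR in the Laboratory Manual; if it does, the gap closes. The documents do not say how many participants fell in the band, and no estimate is offered. No planned efficacy estimate is affected. The consequence for the report is limited to possible under-ascertainment of INR-based liver events at > 3 to ≤ 5×ULN without symptoms.

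**What to change.** **Protocol, if the rule is reused.** In the asymptomatic > 3 to ≤ 5×ULN row of Table 13-4:

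1. Require PT/INR together with the repeat LFT within the week.
2. Require the INR result to be recorded in the CRF, whichever laboratory ran it.
3. State that in anticoagulant users an INR > 1.5 is to be interpreted against the pre-event or therapeutic INR.

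**Study report.** Add one footnote to the SAP Table 5-2 liver summary: INR was not required at > 3 to ≤ 5×ULN without symptoms, so the INR-based liver-event count in that band may be incomplete. Do not add a count of participants tested.

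**Cost.** The protocol change is one extra assay with a repeat test already required, for participants in this band only, plus one recorded result. It has no effect on participants in this trial, because dosing stopped in July 2019. The footnote needs no new data or programming.
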